### Table 8. Summary of Safety Analysis

Safety Evaluation	Incidence	Source Data	Change from Baseline	Shift Baseline	from	Potentially Clinically Significant	Abnormality/ Clinical Significance
ECG = Electrocardiograms;							
X = Safety Assessment will be summarized in tables							
* = Safety As	ssessment wil	ll be listed	in individua	l participar	nt data l	istings	

### 8.4.1. Adverse Events

AEs will be coded using Medical Dictionary for Regulatory Activities (MedDRA) version 24.1. Intensity and relationship of AE will be evaluated by the investigator.

A TEAE is defined as any AE on or after the first dose of IP or any worsening of a pre-existing medical condition/AE with onset after the start of IP and throughout the study. The analysis of AEs will be based on the concept of TEAEs. Where the AE start date is missing, adverse events will be assumed to be treatment-emergent, unless there is clear evidence (through comparison of partial dates) to suggest that the adverse event started prior to the first dose of study treatment. Partial dates will be imputed for AE. The algorithm for missing or partial start /end date is documented in Appendix C.

Adverse events are assigned an AE period based on the onset date/time. AE periods are defined as follows:

- Pre-treatment AE: AE onset date/time before first IP dosing date/time
- TEAE: AE onset date/time on or after the first IP dose date/time (If an AE start date same as IP first dose date, but no time either in AE start or treatment start, then consider this AE to be in treatment period TEAE.)
- On-treatment TEAE: AE onset date/time on or after first IP dose date/time and on or before IP last dose date + 30 days (Note that time does not matter for the end of this period. i.e., if AE occurred after the last dose but on the same date of last dose, it is considered as on-treatment TEAE)
- Post-treatment TEAE: AE onset date on or after IP last dose date + 31 days

An overall summary of TEAEs will include the number and percentage of participants in the following categories:

- Any TEAEs (On-treatment, Post-treatment)
- TEAEs by maximum severity (severe>moderate>mild)
- Any related TEAEs
- Any related TEAEs by maximum severity
- Any serious TEAEs

- Any serious related TEAEs
- Any TEAEs leading to death
- Any TEAEs leading to IP withdrawal
- Any TEAEs leading to withdrawal from the study
- Any TEAEs leading to IP interruption
- Any TEAEs leading to dose reduction before Day 42

Incidence of TEAEs in following categories will be provided by SOC and PT. A participant is counted only once under each SOC and PT in case of multiple occurrences of the same AE. These tables will be sorted by decreasing frequency of System Organ Class (SOC) in SAGE-718 group, then in placebo group, then alphabetically first within SOC then within preferred term.

- TEAEs
- On-treatment TEAEs
- Post-treatment TEAEs
- TEAEs by maximum severity
- TEAEs by causality (related, not related) to IP
- TEAE by maximum severity and causality to IP
- Serious TEAEs
- TEAEs leading to IP withdrawal
- TEAEs leading to withdrawal from the study
- TEAEs leading to IP interruption

Additionally, incidence of TEAEs will be summarized by PT. Most frequent TEAEs reported >5% in PT of any treatment group will also be summarized by PT.

For maximum severity, participants will be counted only once within each SOC and PT at the maximum severity in the following order: severe > moderate > mild; an AE with missing severity will be omitted from severity presentation and will not be imputed. For relationship to IP, participant will be counted only once within each SOC and PT with the strongest relationship to IP in the following order: related > not related; an AE with relationship missing is treated as related. For seriousness, an AE with missing seriousness will not be imputed. The incidences will be presented by descending frequency of SOC and then, within a SOC, by descending frequency of PT based on the participant count, and in alphabetical order of PT if the incidence within a PT is a tie.

In addition, TEAE summary by SOC/PT will also be presented by the following subgroups:

- Race (Black or African American, White, Other)
- Sex (Male, Female)

- BMI ( $\leq 18.4$ , 18.5-24.9, 25-29.9,  $\geq 30$  kg/m^2; categories are defined after rounding)
- Age group ( $\leq 65$ , >65 years)

A by-participant listing of all AEs, SAEs (including those with onset or worsening before the start of IP), AEs leading to death, AEs leading to IP withdrawal through the end of the study, and most frequent (5%) TEAEs will be provided.

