# 12.2. Adverse and Serious Adverse Events

#### 12.2.1. Adverse Event Definition

An AE is any untoward medical occurrence in a patient or clinical investigation participant administered a pharmaceutical product and that does not necessarily have a causal relationship with this treatment. An AE can therefore be any unfavorable and unintended sign (including an abnormal laboratory finding), symptom or disease temporally associated with the use of a medicinal (investigational) product whether or not related to the medicinal (investigational) product. In clinical studies, an AE can include an undesirable medical condition occurring at any time, including baseline or washout periods, even if no IP has been administered. A TEAE is defined as an AE with onset after the start of IP, or any worsening of a pre-existing medical condition/AE with onset after the start of IP and throughout the study. The term IP includes any Sage IP, a comparator, or a placebo administered in a clinical study.

Laboratory abnormalities and changes from baseline in vital signs, and ECGs are considered AEs if they result in discontinuation or interruption of IP, require therapeutic medical intervention, meet protocol specific criteria (if applicable) or if the Investigator considers them to be CS. Any abnormalities that meet the criteria for a SAE should be reported in an expedited manner. Laboratory abnormalities and changes from baseline in vital signs and ECGs that are clearly attributable to another AE do not require discrete reporting (eg, electrolyte disturbances in the context of dehydration, chemistry and hematologic disturbances in the context of sepsis).

All AEs that occur after any participant has signed the informed consent and throughout the duration of the study, whether or not they are related to the study, must be reported to Sage Therapeutics.

Participants who discontinue the IP due to an AE, regardless of Investigator-determined causality, should be followed until the event is resolved, considered stable, or the Investigator determines the event is no longer CS. Any AEs that are unresolved at the participant's last AE assessment in the study are followed up by the Investigator for as long as medically indicated, but without further recording in the eCRF. The Sponsor or its representative retains the right to request additional information for any participant with ongoing AE(s)/SAE(s) at the end of the study, if judged necessary.

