#### 13.6.1. Adverse Events

A TEAE is defined as an AE with onset after the first dose of IP. The analysis of AEs will be based on the concept of TEAEs. The incidence of TEAEs will be summarized by system organ class and preferred term. In addition, summaries will be provided by intensity (mild, moderate, severe) and by causality (related, not related) to IP.

Any TEAEs leading to discontinuation or interruption of treatment or withdrawal from the study and any treatment-emergent SAEs will be summarized.

All AEs and SAEs (including those with onset or worsening before the start of IP) through the end of the study will be listed.

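### SAP 8.4.1 has two conflicting TEAE rules: the definition counts worsening of a pre-dose AE, but the AE-period rules go by onset date alone

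*SAP*

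**What the plan says.** SAP 8.4.1 opens with a definition in two parts. A TEAE is an AE from the first dose onward, or "any worsening of a pre-existing medical condition/AE with onset after the start of IP and throughout the study". The AE tables are to be built on TEAEs.

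The same section then gives derivation rules: "Adverse events are assigned an AE period based on the onset date/time". The list that follows has four entries:

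- "Pre-treatment AE: AE onset date/time before first IP dosing date/time"
- "TEAE: AE onset date/time on or after the first IP dose date/time"
- "On-treatment TEAE: AE onset date/time on or after first IP dose date/time and on or before IP last dose date + 30 days"
- Post-treatment TEAE, with onset from 31 days after the last dose.

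None of the four mentions worsening. The missing-date rule in SAP 8.4.1 also looks only at when the AE started.

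The protocol has the same split. Section 12.2.1 adds worsening to its definition ("or any worsening of a pre-existing medical" condition or AE). Section 13.6.1, the statistical section, does not: "A TEAE is defined as an AE with onset after the first dose of IP". SAP 6.1 lists no modification from the protocol.

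**The concern.** The list in SAP 8.4.1 contains an entry that is itself labelled TEAE and is narrower than the definition a few lines above it. The SAP does not say which of the two sets the flag for the TEAE tables, so two programmers working from the same text could derive different TEAE counts.

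The proportion of participants with TEAEs, and TEAE severity, are secondary endpoints (Protocol Section 6, SAP 4.2). The AEs at risk are those that began before dosing and became worse on treatment. If SAGE-718 aggravates an existing symptom, this is where the effect would show.

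The situation can arise because AEs are collected from consent onward (notes to the Schedule of Assessments), and screening and baseline can take up to 35 days before first dose.

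**Working it through.** The plan states no figure for this point, so the check is to apply each rule in SAP 8.4.1 to the ways a worsened AE could be recorded. As an illustration, suppose mild dizziness starts on Day -10 and becomes severe on Day 12.

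| How it is recorded | Definition sentence | Period list | On- or post-treatment TEAE table | Main TEAE tables |
|---|---|---|---|---|
| A. One AE record, onset Day -10 | TEAE (worsened after first dose) | Pre-treatment (Day -10 is before Day 1) | Neither | Depends on which rule is programmed |
| B. New AE record at worsening, onset Day 12 | TEAE | TEAE | On-treatment | Included |
| C. Baseline medical condition that worsens and is entered on the AE form with a post-dose onset (SAP 8.4.5) | TEAE | TEAE | By its onset date | Included |

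The two rules disagree only in case A. There the exclusion from the on-treatment and post-treatment tables is definite, because both of those entries require onset at or after first dose. Exclusion from the main tables is conditional on the period flag driving them.

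The next question is whether the documents rule out case A. Protocol 12.2.5 asks for an onset date, a resolution date and an intensity for each AE, and says nothing about opening a new record when an ongoing AE worsens. SAP 8.4.5 sends worsened baseline conditions to the AE form, but it belongs to the physical-examination section, gives no onset-date rule, and does not address an AE that has been on the form since consent. Nothing in the visible text rules out case A.

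**Size.** The documents give no AE rates. The longest nominal pre-dose share of AE collection is 35 / (35 + 84 + 28) = 35/147 = 23.8% of days. That is an upper limit on time and does not count affected events. For scale only, assume that 5% to 15% of participants have an AE starting between consent and first dose, and that 5% to 20% of those AEs worsen after dosing. With 75 randomized per arm:

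- low: 75 × 0.05 × 0.05 = 0.19 participants per arm
- middle: 75 × 0.10 × 0.10 = 0.75
- high: 75 × 0.15 × 0.20 = 2.25

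Both sets of rates are assumptions. The range shows only that the count is likely to be small, and it applies only to worsenings kept as a single record.

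**The case against.** The strongest reply is that the definition gives worsening an onset of its own: "any worsening of a pre-existing medical condition/AE with onset after the start of IP and throughout the study" can be read as dating the worsening itself. On that reading a worsening on Day 12 has a post-dose onset, and the period rules capture it. The reply is fair if each worsening has its own record, which is case B. It does not help a single record whose only onset date is before dosing. The reading is also weakened by Protocol 13.6.1 and SAP 8.4.1, which both describe listings of AEs with onset or worsening before IP and so treat the two as different things.

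A second reply is that recording practice is out of view. The eCRF and the Appendix C date algorithm are not shown, and if the eCRF opens a new record at worsening, nothing is lost. This stands as a limit on the finding. The absence of that material is not itself an error in the plan.

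A third reply is that the consequence is modest. Safety is summarized without hypothesis testing (SAP 8.4), and the listing of all AEs includes every event whatever its period. Both points stand, but the TEAE summaries are still the secondary endpoints.

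A reader might go further and infer that every pre-dose AE that worsens on drug is lost from the TEAE tables. The documents do not support that. It would require both a single record and a period flag that overrides the definition in the main tables, and neither is stated. A reader might also object that the on-treatment and post-treatment rows would not add up to all TEAEs. That carries little weight: the rows count participants, and one person can be in both.

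**Conclusion.** The conflict in SAP 8.4.1 is real, and Protocol 12.2.1 and 13.6.1 repeat it. An AE that begins before first dose, worsens afterwards and stays as one record is a TEAE under the definition and pre-treatment under the period list. For such a record, exclusion from the on-treatment and post-treatment TEAE tables is certain. Exclusion from the main incidence, severity and causality tables is possible and depends on which rule is programmed.

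The number affected cannot be derived from the documents. Under the assumed rates above it is about 0.2 to 2.3 participants per arm. The ambiguity touches a secondary endpoint and is cheap to remove, so it should be corrected before database lock.

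**What to change.** In SAP 8.4.1, state one rule and use it for both the definition and the periods:

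- An AE with onset before first dose that worsens on or after first dose is a TEAE. It is assigned to the on-treatment or post-treatment period by the date of first post-dose worsening, or by the onset date of the new record if worsening is entered as a new AE.
- Pre-treatment AE is limited to AEs with onset before first dose and no worsening afterwards.

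Align Protocol 13.6.1 with 12.2.1, or record in SAP 6.1 that the SAP definition applies.

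The cost is a few lines of text and a small programming change. If the eCRF holds no worsening date, sites also need a data-entry instruction to open a new AE record at worsening. The TEAE proportion may rise slightly in both arms.

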## 5.1. Overall Risk/Benefit Assessment

In addition to the study discussed above, SAGE-718 has been shown to improve cognition in other neurodegenerative disorders (for details refer to SAGE-718 Investigator's Brochure [IB]). The potential benefit of SAGE-718 is coupled with low risk of NMDAR-associated excitotoxicity. Indeed, SAGE-718 is oxysterol-based and acts on the 24(S) hydroxycholesterol (24SHC) binding site of NMDAR. SAGE-718 only modulates the response of NMDAR in the presence of endogenous glutamate. That is, SAGE-718 does not directly activate the receptor and thus, is not expected to cause NMDAR-associated glutamatergic excitotoxicity.

SAGE-718 has been well characterized in a comprehensive series of in vitro and in vivo nonclinical studies that have defined its key pharmacology, absorption, distribution, metabolism and excretion (ADME), drug-drug interaction, and toxicology findings, including compound-related effects and the reversibility of these changes. In a radiolabeled rat ADME study, there

was no selective distribution or retention of radioactive SAGE-718 to pigmented tissues and no quantifiable concentration of radioactivity was observed in the eye lens in Long Evans rats, implying that potential risk of phototoxicity is low.

Due to an unexplained mortality early in the 14-day oral repeat-dose rat study at 30 mg/kg/day, a human maximum concentration ( $C_{max}$ ) cap for clinical studies was established from the Day 0 mean  $C_{max}$  (443 ng/mL) in female rats at the 15 mg/kg/day dose level. A 10-fold safety factor was used to derive the 45 ng/mL clinical exposure cap (see Section 5.2 Dose Justification). Across the nonclinical studies conducted with rats and dogs, a  $C_{max}$  threshold for observation of convulsions occurred at exposures 20 to 40 times greater than clinically relevant exposures.

No deaths, SAEs or TEAEs leading to discontinuation assessed as related to SAGE-718 were reported in the completed studies with SAGE-718. A maximum tolerated dose has not been identified and no characteristic safety signals have been identified to date. No clinically relevant mean changes from baseline have been observed in ECGs or EEGs. In addition, there were no SAEs or severe TEAEs reported in patients with AD that were enrolled in the completed Study 718-CNA-201.

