### 4.2. Safety Endpoints

- To evaluate the safety and tolerability of SAGE-718 softgel lipid capsule in participants with AD
  - Proportion of participants experiencing treatment-emergent adverse events (TEAEs) and severity of TEAEs
  - Number of participants who withdraw due to adverse events (AEs)
- To evaluate the safety and tolerability of SAGE-718 softgel lipid capsule on other safety parameters
  - Change from baseline in vital signs, clinical laboratory parameters, electrocardiograms (ECGs),

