# 8. STATISTICAL ANALYSIS

# 8.1. General Considerations

Continuous data will be summarized in terms of the number of participants, mean, standard deviation (SD), minimum value (min), maximum value (max), median, 25th percentile (Q1), and 75th percentile (Q3). The minimum and maximum will be reported with the same number of decimal places as the source (raw) data. Mean, Least squares Means (LSM), median, Q1 and Q3 will be reported to 1 decimal place more than the source (raw) data. SD and standard error (SE), if applicable, will be reported to 2 decimal places more than the source (raw) data. Any values that require transformation to standard units (metric or SI) will be converted with the appropriate corresponding precision. Confidence intervals (CI) will be presented to one more decimal place than the associated parameter estimate. In general, the maximum number of decimal places reported shall be four for any summary statistic.

Categorical data will be summarized in terms of the number of participants providing data at the relevant time point (n), frequency counts, and percentages. Percentages will be presented to 1 decimal place unless otherwise specified. Any planned collapsing of categories will be detailed in the SAP text and the data displays.

Percentages will not be presented for zero counts. Percentages will be calculated using the number of participants (n) as the denominator. A missing category shall be included only for categorical variables where no data is available. The missing category will be omitted if there are no missing values for that variable.

Participants who are randomized to 1.2 mg treatment and received 0.9 mg dose due to dose reduction will be summarized under the same SAGE-718 treatment group. For efficacy data analysis, participants' data are analyzed by randomized treatment. For safety data analysis, participants' data are analyzed per the actual treatment received, and this is determined as follows: if a participant received any dose of SAGE-718 at any point of time, the participant is assigned to actual treatment of SAGE-718, regardless of the treatment to which the participant has been randomized.

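### AEs with missing severity drop out of the SAP's severity rows, so the severity part of the secondary safety endpoint can be understated but never overstated

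*SAP*

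**What the plan says.** SAP 4.2 gives the first safety endpoint as "Proportion of participants experiencing treatment-emergent adverse events (TEAEs) and severity of TEAEs", and SAP 8.4 ties the secondary objective to the frequency and severity of TEAEs.

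SAP 8.4.1 sets the counting rule, "For maximum severity, participants will be counted only once within each SOC and PT at the maximum severity", in the order severe, moderate, mild. It then says that "an AE with missing severity will be omitted from severity presentation and will not be imputed". The section asks for no missing row, footnote or count of ungraded events.

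The same section has three other rules for missing AE fields:
- Relationship: "an AE with relationship missing is treated as related".
- Start date: "Where the AE start date is missing, adverse events will be assumed to be treatment-emergent, unless there is clear evidence".
- Seriousness: "For seriousness, an AE with missing seriousness will not be imputed".

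The general default in SAP 8.1 and Protocol 13.2 is that missing data are not imputed. SAP 8.1 also mentions a missing category: "The missing category will be omitted if there are no missing values for that variable". The sentence before it limits that category to categorical variables for which there are no data. Protocol 12.2.5 has the investigator report intensity for every AE.

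**The concern.** A maximum can be taken only over the grades that are known. If ungraded events are removed first, the result is labelled as the participant's maximum when it is only the highest recorded grade. Where there is no recorded grade at all, the participant leaves the severity rows with nothing to mark the gap.

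Both effects run the same way. Removing an event can lower a participant's reported maximum or remove the participant, but can never raise it. At stake is whether the severity half of a named secondary endpoint can be read at face value and reconciled with the TEAE total.

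**Working it through.** The plan gives no figure on this point to reproduce, so the check applies the rule to simple cases.

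**Inputs.** The counting and omission rules come from SAP 8.4.1. The planned 75 per group comes from SAP 5.2 and is used only for scale. The number of ungraded TEAEs is not in the documents; 0 to 5 affected participants per arm is assumed. Percentages are assumed to use all 75 in the arm as denominator.

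**Step 1: rule applied to one participant**

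| Participant's TEAEs | Shown under 8.4.1 | What is known about the maximum |
|---|---|---|
| ungraded only | absent | unknown |
| mild + ungraded | mild | at least mild |
| severe + ungraded | severe | severe |

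Only the third case is reported correctly for certain. The same holds within each SOC and PT.

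**Step 2: size per participant.** The shift in a severity row is m/75 for m affected participants: 0 gives 0; 1 gives 1.33; 2 gives 2.67; 3 gives 4.00; 5 gives 6.67 percentage points.

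**Step 3: whether rows add up.** Take a hypothetical arm of 75 with 40 TEAE participants, whose true maximum is mild in 24, moderate in 12 and severe in 4.
- If one of the 4 has only an ungraded TEAE, the severe row shows 3/75 = 4.0% instead of 4/75 = 5.3%. The rows sum to 24 + 12 + 3 = 39 against 40 with any TEAE.
- If two of the 4 do, the severe row shows 2/75 = 2.7% and the rows sum to 38.
- If instead one of the 24 shown as mild also has an ungraded event, the rows still sum to 40. Nothing in the table signals that this participant's maximum is unknown.

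**Step 4: same arm with a Missing row ranked below severe and above moderate and mild.** The first case becomes 24 + 12 + 3 + 1 Missing = 40. The second becomes 24 + 12 + 2 + 2 Missing = 40. The third becomes 23 + 12 + 4 + 1 Missing = 40. The total reconciles each time and no grade has been invented.

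**Step 5: severity crossed with causality.** An event missing both fields counts as related under one rule and leaves the severity split under the other. The related-TEAE severity rows then need not sum to the related total.

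**The case against.** The strongest reply is that this is a display convention with a hypothetical effect. Protocol 12.2.5 requires intensity for each AE, and Protocol 14.1 has monitors confirm that AEs are properly documented, so blanks should be rare. Ungraded events stay in overall TEAE incidence, the SOC/PT tables, the related, serious, withdrawal, interruption and dose-reduction summaries where they qualify, and the AE listing. A severe event may also show up elsewhere, since the protocol's definition mentions stopping IP or hospitalization. All of this stands and keeps the point small. It does not justify a rule that, in the very case it was written for, can err in only one direction.

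Some stronger readings are tempting but unsupported:
- A reader might infer that severity alone is handled leniently in 8.4.1. Missing seriousness is not imputed either, and no imputation is the plan's default; relationship and start date are the exceptions.
- A reader might infer a contradiction with SAP 8.1. Its two sentences on a missing category are unclear when read together, and 8.4.1 is the more specific rule.
- A reader might infer from the prior AD study, where "there were no SAEs or severe TEAEs reported in patients with AD", that severe counts will be close to zero and a single omission decisive. That study had 24 participants and 14 days of open-label dosing, which does not establish the count over 12 weeks.
- A reader might conclude that blanks should count as severe. That could only raise severity, which is the mirror-image bias, and it imputes a value against the plan's default.

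**Conclusion.** The point holds as a minor reporting gap. Whenever the omission rule is triggered, the severity rows can understate a participant's maximum grade or leave the participant out, and they may not add to the TEAE total. They cannot overstate severity.

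The size is 1.3 percentage points of a 75-person arm per affected participant, and zero if every TEAE is graded. The documents do not give the number of missing grades, and the requirement to record intensity suggests it will be small. The proportion-with-TEAEs half of the endpoint is untouched, so it would be wrong to infer that participants are lost from the endpoint as a whole.

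**What to change.** In SAP 8.4.1, keep the no-imputation rule but replace the omission with a display rule, for example:

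> *A TEAE with missing severity is not imputed and is shown in a Missing category. For maximum severity, a participant with any severe event is counted as severe. Otherwise a participant with any ungraded event is counted as Missing, ahead of moderate and mild.*

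Apply it to all maximum-severity summaries, including the related-TEAE and causality splits, in Tables 14.3.1.1 and 14.3.1.3. The rows then add to the TEAE total.

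The cost is one sentence and one extra row, shown only if needed. The small downside is that a few participants with a known lower grade will appear as Missing. The change is best made before database lock, because SAP section 2 requires later changes to be documented and discussed in the clinical study report.
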